
12.7. Appendix 7: Reporting Standards for Missing Data

12.7.1. Premature Withdrawals

Element	Reporting Detail
General	
 • Subject study completion (i.e. as specified in the protocol) was defined as completing the 12-week treatment period and three month safety follow up. • Withdrawn participants were not replaced in the study. • All available data from participants who were withdrawn from the study will be listed and all available planned data will be included in summary tables and figures, unless otherwise specified.

12.7.2. Handling of Missing Data

Element	Reporting Detail
General	
 • Missing data occurs when any requested data is not provided, leading to blank fields on the collection instrument: 
 ○ These data will be indicated by the use of a “blank” in subject listing displays. Unless all data for a specific visit are missing in which case the data is excluded from the table. ○ Answers such as “Not applicable” and “Not evaluable” are not considered to be missing data and should be displayed as such.
Analysis	
 • All missing data will be handled according to estimand of interest as described within the main body of the RAP.
ACQ-5	
 • If one of the five items in the ACQ-5 is missing then the response from the four remaining items will be interpolated (pro-rata) to gain the overall response for the participant. • If more than one item is missing then the ACQ-5 will be considered missing.
AQLQ	
 • The AQLQ contains 32 items in four domains: activity limitation (11 items), symptoms (12 items), emotional function (five items), and environmental stimuli (four items). For the overall score, there must be no more than three missing responses (and never more than one per domain). The symptom and activity domain scores can have up to one missing value per domain, but for the emotional function and environmental stimuli domain scores must have no missing responses. • If there are missing values at a visit (for example visit 2) then data will be imputed using data from both this visit and the previous study visit (for example visit 1) as shown below: Visit 1 (completed data): Total score = A Visit 2 (incomplete data): Total score = B Visit 2 imputed score: B/A x 2

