12.2. Appendix 2: Schedule of Activities

12.2.1. Protocol Defined Schedule of Events

Procedure	Screening (±5days)	Run-in (±5days)	Treatment Period (Visit window ±3days)				End of Treatment / EW (±3days)	FU (±3days)	Notes
			V3	V4	V5	V6			
Visit	V1	V2	V3	V4	V5	V6	V7	V8	
Week	-4	-2	0	2	4	8	12	24	
Day	-28	-14	1	15	29	57	85	169	
Informed consent	X								May be obtained prior to Screening.
Inclusion and exclusion criteria	X	X	X						Recheck clinical status before 1 st dose of study medication.
Demography	X								
Full physical examination	X								To include height and weight
Medical/medication/ drug/alcohol/smoking history	X								Including smoking history, substance abuse, medical conditions and family history of premature cardiovascular disease; asthma disease duration and exacerbation history
Human immunodeficiency virus (HIV), Hepatitis B and C screening	X								If test otherwise performed within 3 months prior to first dose of study treatment, testing at screening is not required
Genetics									
Informed consent for Pharmacogenetic blood sample		X							

Procedure	Screening (±5days)	Run-in (±5days)	Treatment Period (Visit window ±3days)				End of Treatment / EW (±3days)	FU (±3days)	Notes
			V3	V4	V5	V6			
Visit	V1	V2	V3	V4	V5	V6	V7	V8	
Week	-4	-2	0	2	4	8	12	24	
Pharmacogenetic (PGx) blood sample			X						PGx sample may be drawn any time from Visit 3 onwards, pre-dose. Informed consent must be obtained before collecting a sample.
Study Treatment and Questionnaires									
Randomisation			X						
Study treatment			X		X	X			
Dispense diary card		X							To be completed daily.
Diary card review			X	X	X	X	X		
Collect diary card							X		
Rescue medication dispensing		X	X ¹	X ¹	X ¹	X ¹			1. As needed
ACQ-5	X		X	X	X	X	X		Test to be performed before all other assessments
AQLQ			X	X	X	X	X		Test to be performed immediately after ACQ-5
Efficacy									
Haematology (including eosinophil count)	X		X ¹	X	X	X	X		1. Pre-dose
FeNO	X		X	X	X	X	X		Test to be performed pre-dose
Spirometry	X		X	X	X	X	X		Test to be performed pre-dose

Procedure	Screening (±5days)	Run-in (±5days)	Treatment Period (Visit window ±3days)				End of Treatment / EW (±3days)	FU (±3days)	Notes
			V3	V4	V5	V6			
Visit	V1	V2	V3	V4	V5	V6	V7	V8	
Week	-4	-2	0	2	4	8	12	24	

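### The AQLQ missing-item rule relies on a completed previous visit, so an incomplete but acceptable Day 1 form, the only planned baseline, has no usable calculation

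*SAP*

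**What the plan says.** SAP 12.7.2 (AQLQ row) makes two statements about incomplete forms.

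- **Tolerance.** "For the overall score, there must be no more than three missing responses (and never more than one per domain"). The domain scores have limits of their own: one gap is allowed in each of symptoms and activity limitation, while any gap in emotional function or environmental stimuli invalidates that domain's score.
- **Calculation.** When responses are missing at a visit, "data will be imputed using data from both this visit and the previous study visit". The illustration sets "Visit 1 (completed data): Total score = A", calls the incomplete later total B, and ends with "Visit 2 imputed score: B/A x 2".

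The ACQ-5 row of the same table works differently. With one item missing, "the response from the four remaining items will be interpolated (pro-rata) to gain the overall response for the participant", so only the current visit is needed.

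The baseline table in SAP 5.2 marks AQLQ at Day 1 pre-dose only. The schedule in SAP 12.2.1 has AQLQ ("Test to be performed immediately after ACQ-5") at V3 to V7, that is Weeks 0, 2, 4, 8 and 12, and not at screening or run-in. SAP 7.2.1 keeps AQLQ change from baseline and AQLQ response as secondary endpoints. SAP 12.10.5 displays them in Tables 2.07 (total score) and 2.08 (responders).

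**The concern.** The tolerance and the calculation do not fit together at the visit that matters most. The tolerance says that a Day 1 form with a few gaps still yields an overall score. The calculation needs a completed earlier AQLQ, and none is planned before Day 1. Every change and responder value for the total score is measured against that Day 1 total.

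Two programmers could therefore reasonably do different things: average the answered items, or treat the total as missing because the stated method cannot be run. Under the second choice the participant disappears from Tables 2.07 and 2.08 at all four post-baseline weeks. SAP 2.1 says that 20 randomised subjects were not reached, so one lost participant would be noticeable even in a descriptive table.

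**Working it through.** No figure in the plan needs reproducing except the item count: 11 + 12 + 5 + 4 = 32, as stated in SAP 12.7.2.

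**1. Is there an input at Day 1?** The rule needs A, a completed total from the previous study visit. Planned AQLQ forms before Day 1 (SAP 5.2 and 12.2.1): zero. A does not exist.

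**2. Does another provision fill the gap?**

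- The baseline rule in SAP 5.2 takes the latest non-missing pre-dose value, including unscheduled ones. No earlier AQLQ is planned, whereas ACQ-5, FeNO, eosinophils and FEV1 also have a screening value.
- The general analysis row of SAP 12.7.2 refers missing data to the estimand in the main body. SAP 7.1 and 7.2 say only that no intercurrent events are considered, which is not a scoring rule.

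**3. Does the gap carry forward?** Yes. An incomplete Day 1 form is not completed data, so it cannot serve as A for an incomplete Week 2 form. A missed or incomplete form at any later visit has the same effect on the next one.

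**4. Does the formula work where A exists?** Take two participants whose every answer is unchanged, with one item skipped at the later visit.

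- Item mean 5: A = 32 × 5 = 160, B = 31 × 5 = 155, so B/A × 2 = 1.94.
- Item mean 3: A = 32 × 3 = 96, B = 31 × 3 = 93, so B/A × 2 = 1.94.

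The result is close to 2 whatever the score level, so the printed line does not return a score on the scale of A and B. It has to be replaced in any case, but correcting it alone would still leave Day 1 without a rule.

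**5. Which incomplete Day 1 forms fall in the gap?** A single skipped item is always within the overall-score tolerance. It is within the domain tolerance for 11 + 12 = 23 of 32 items (72%). For the other 5 + 4 = 9 items (28%), that one domain score is invalid and the other three domains are complete.

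For several skipped items, assume independent skipping at a per-item rate p. These rates are assumptions; the SAP gives none. The chance of at least one gap is 1 − (1 − p)^32. The chance of one to three gaps with at most one per domain comes from combining, over the four domains of size n, the probabilities of no gap, (1 − p)^n, and of one gap, n·p·(1 − p)^(n−1).

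| Assumed p | At least one gap | Gap, within tolerance | Share of incomplete forms within tolerance |
|---|---|---|---|
| 0.1% | 3.2% | 3.1% | 99.6% |
| 0.5% | 14.8% | 14.5% | 97.8% |
| 1% | 27.5% | 26.2% | 95.3% |
| 2% | 47.6% | 42.8% | 89.9% |

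The last column is the useful one. Under these assumptions, about 90% or more of incomplete Day 1 forms would be ones the SAP accepts but cannot calculate.

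**The case against.** The strongest reply is that the SAP never says an incomplete Day 1 total is lost. Its tolerance keeps the overall score usable, and a sensible programmer would average the answered items. That stands as a limit on the point.

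Several stronger readings are tempting, and the document does not support them:

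- A reader might infer that one skipped baseline item removes all of a participant's AQLQ results. Loss follows only from an unstated programming choice, and domain scores with no missing item can still be calculated.
- A reader might multiply the chance of a gap by a sample size to get an expected number of lost baselines. The SAP gives neither a skip rate nor the number randomised, and a form with a gap is not a lost score when the tolerance accepts it.
- A reader might infer that using the previous visit pulls change towards zero. The ratio B/A moves with the current answers, and A is in the denominator, so this is not shown.
- A reader might see a conflict because no AQLQ is scheduled at V1 or V2. The SAP labels those visits as examples, so they can be read as any two consecutive visits.

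It is also fair to say that the consequence is limited: AQLQ is secondary, and SAP 2.4 makes every summary descriptive. Finally, the SAP does not show that the mean of answered items is this instrument's own scoring rule.

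What the reply does not remove is that a stated rule cannot be run at the only planned baseline visit, and nothing else in the SAP replaces it.

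**Conclusion.** The point holds as a gap in the scoring rule. A Day 1 AQLQ form that SAP 12.7.2 accepts has no usable calculation, and the same failure recurs whenever the preceding form is missed or incomplete. The text alone establishes this, without the assumed skip rates.

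The effect is conditional. If an incomplete Day 1 total is set to missing, that participant leaves the total-score change and responder summaries at Weeks 2, 4, 8 and 12. The number affected is unknown, with fewer than 20 randomised as the ceiling, and is nil if data capture prevents skipped items. No inference is at stake, but the tables should not depend on a programmer's choice. It should be settled before unblinding.

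**What to change.** In the AQLQ row of SAP 12.7.2, delete the previous-visit rule together with its illustration and formula. Replace it with one within-visit rule for every visit including Day 1:

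- **Overall score:** with at most three missing responses and at most one per domain, the mean of the answered items; otherwise missing.
- **Symptom and activity domains:** with at most one missing response, the mean of the answered items in that domain; otherwise missing.
- **Emotional function and environmental stimuli domains:** missing if any response is missing, as now. A single gap here does not invalidate the overall score.

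Confirm the rule against the instrument's scoring instructions before adopting it.

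The cost is a change of SAP wording and simpler programming, in line with the ACQ-5 rule. The downside is that incomplete forms no longer draw on the previous visit. That loss is small with at most one missing item per domain. If items are scored over a range of 6 points (an assumption; the SAP gives no item range), one skipped item moves the overall mean by at most 6/32 = 0.19, against the 0.5 responder threshold. Three skipped items could move it by at most 3 × 6/32 = 0.56, and only if each differed from all the answered items by the full range.

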5.2. Baseline Definitions

For all endpoints (except as noted in baseline definitions) the baseline value will be the latest pre-dose assessment with a non-missing value, including those from unscheduled visits. If time is not collected, Day 1 assessments are assumed to be taken prior to first dose and used as baseline.

Parameter	Study Assessments Considered as Baseline			Baseline Used in Data Display
	Screening	Run-in	Day 1 (Pre-Dose)	
Primary Endpoints				
Fractional Exhaled Nitric Oxide (FeNO)	X		X	Day 1
Blood Eosinophils	X		X	Day 1
Other Patient Reported Outcomes				
AQLQ			X	Day 1
Asthma Control Questionnaire (ACQ-5) score	X		X	Day 1
Spirometry				
Forced Expiratory Volume (FEV1)	X		X	Day 1
Pharmacodynamics				
Free and total sST2 (serum)			X	Day 1

Parameter	Study Assessments Considered as Baseline			Baseline Used in Data Display
	Screening	Run-in	Day 1 (Pre-Dose)	
Safety				
Vital Signs	X	X	X	Day 1
12-lead Electrocardiogram (ECG) measurements	X		X	Day 1
24 hours Holter measurements		X	X	Day 1
Clinical laboratory tests (haematology and chemistry)	X		X	Day 1
Immunogenicity: Anti-GSK3772847 antibodies			X	Day 1
Biomarkers				
Induced sputum biomarkers		X	X	Run-in ¹
Exploratory serum markers (including IgE and Fungal-specific IgE)	X		X	Day 1

NOTES:

- Unless otherwise stated, the mean of replicate assessments taken on the same day will be used as the value for that day.
- ¹ Baseline is taken at run-in. If the sputum taken at run-in is not viable then a sample is taken at Day 1 (Pre-Dose) and is used as baseline.

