7.2. Secondary Efficacy Analyses

7.2.1. Endpoint and Summary Measure

Secondary Endpoints	Summary Measure

 Change from baseline (Week 0) in spirometry parameters over time including but not limited to pre-bronchodilator Forced expiratory volume in 1 second. Change from baseline (Week 0) in Asthma Control Questionnaire -5 absolute score at Weeks 2, 4, 8 and 12 Change from baseline (Week 0) in Asthma Quality of Life Questionnaire total and domain scores at Weeks 2, 4, 8 and 12 	Summary statistics (raw and change from baseline)

 Proportion of responders to ACQ-5. A responder to ACQ-5 will be defined as a subject who has a decrease from baseline in ACQ-5 score of 0.5 or more at Weeks 2, 4, 8 and 12. Proportion of responders to AQLQ. A responder to AQLQ will be defined as a subject who has an increase from baseline in AQLQ score of 0.5 or more at Weeks 2, 4, 8 and 12. 	Number and percentage of responders

Secondary efficacy summaries will be based on the mITT population and no intercurrent events will be considered.

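### The AQLQ missing-item formula multiplies by an undefined 2 and does not name the score it produces: it is wrong if taken literally, ambiguous otherwise, and has no input at Week 0.

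*SAP*

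**What the plan says.** The AQLQ row of SAP section 12.7.2 describes 32 items in four domains (activity 11, symptoms 12, emotional function 5, environment 4). An overall score may have at most three missing answers and at most one per domain. The symptom and activity domain scores may each have one missing answer; the other two domain scores may have none.

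Where values are missing, "data will be imputed using data from both this visit and the previous study visit". A is the total score at the earlier, complete visit. The later visit is given as "Visit 2 (incomplete data): Total score = B". The result is "Visit 2 imputed score: B/A x 2". Nothing else is said about the calculation.

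The ACQ-5 row of the same table says plainly what is computed when one item is missing: "the response from the four remaining items will be interpolated (pro-rata) to gain the overall response for the participant".

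Section 5.2 states that "the baseline value will be the latest pre-dose assessment with a non-missing value", and for AQLQ it lists only the Day 1 assessment. The schedule in section 12.2.1 shows AQLQ first collected at V3 (Week 0). Section 7.2.1 defines an AQLQ responder by an "increase from baseline in AQLQ score of 0.5 or more at Weeks 2, 4, 8 and 12". Tables 2.07 and 2.08 report the total score and the responders.

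**The concern.** B/A is a ratio of two totals and has no units. Multiplied by 2 it becomes a score only if the 2 is itself a score, and the SAP never says what the 2 is. It also does not say whether the result replaces a missing item or the total, or whether A covers all 32 items or only those answered at the later visit. Two programmers could both follow the line and derive different AQLQ scores.

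Taken literally, the line does more than leave a choice open: a patient whose answers do not change has each missing item set to about 2, whatever their level. AQLQ change and AQLQ response are secondary endpoints, and the responder count is the more sensitive because it depends on a 0.5 cut-off.

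The rule also needs an earlier AQLQ. At Week 0 there is none, so a baseline form with a permitted missing item has no usable rule, and every later change for that patient depends on that baseline.

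**Working it through.** **Inputs from the SAP.** Item count 11 + 12 + 5 + 4 = 32, which agrees with the stated 32. At most three missing items for the total. Formula (B/A) × 2. Responder threshold 0.5. There is no worked figure in the plan to reproduce.

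**Assumptions.** The total is the mean of the items; the SAP does not say so, but the 0.5 threshold is consistent with it. The illustrative patient has mean 4.5 at the previous visit and answers 5 to every answered item at the current visit, so the true current total is 5.

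**Reading 1: 2 is a constant and the result is an item.**
- A and B as means, one item missing: 2 × 5/4.5 = 2.222. Total = (31 × 5 + 2.222)/32 = 4.913. Bias = (2.222 − 5)/32 = −0.087.
- Three items missing: 3 × (2.222 − 5)/32 = −0.260.
- A as the 32-item sum (4.5 × 32 = 144) and B as the sum of answered items. One missing: 2 × 155/144 = 2.153, bias (2.153 − 5)/32 = −0.089. Three missing: 2 × 145/144 = 2.014, bias 3 × (2.014 − 5)/32 = −0.280.
- Responder status at Week 2, where A is normally the baseline: true change 5 − 4.5 = +0.50; recorded change 4.913 − 4.5 = +0.41. A responder becomes a non-responder. In this example the flip needs a true change no more than about 0.09 above the threshold (one item), or 0.26 to 0.28 (three items).
- Arm mean, assuming 5 to 9 subjects per arm (section 2.1 supports only fewer than 20 randomised): one such form shifts it by 0.087/9 = 0.010 to 0.089/5 = 0.018 (one item), or 0.260/9 = 0.029 to 0.280/5 = 0.056 (three items).

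**Reading 2: 2 stands for the missing item's own previous response.**
- Same items in A and B, previous response 4.5: (5/4.5) × 4.5 = 5.0. Total 5.0, bias 0.
- Unmatched sums, patient stable at 5. One missing: (31/32 − 1) × 5/32 = −0.005. Three missing: 3 × (29/32 − 1) × 5/32 = −0.044.

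**Week 0.** The first AQLQ is at V3, so A does not exist and neither reading yields a value.

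**The case against.** The strongest reply is that the effect is close to nil. All data are summarised descriptively (section 2.4), AQLQ is secondary, few answers may be missing before a score is void, and nothing shows that any form had a missing item. The likely intent is Reading 2, an example value whose label was left out, and that rule is nearly unbiased. A label could also have been lost when the table was read from PDF, although the cell otherwise looks intact. All of this stands and limits the point. It does not supply the definition: the SAP nowhere states Reading 2.

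Two stronger readings should be resisted. A reader might infer that the line cannot be applied at all. That goes too far: it can be computed after Week 0, but in more than one way.

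A reader might also take the result as the total score. Any stable patient would then score 2 × x/x = 2, and A = 4.5 with B = 5.2 would give 2 × 5.2/4.5 = 2.31, turning a true +0.7 into −2.19. The documents do not support this as the working interpretation. The introductory sentence speaks of missing values being imputed, which fits an item, and such totals would probably be noticed in programming checks. That figure should not be used as the size of the problem.

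**Conclusion.** The point holds in limited form. The formula gives a wrong item score if the 2 is taken as a constant, and is ambiguous otherwise, because neither the multiplier nor the imputed quantity is defined. For the illustrative patient the bias in the mean-item total is −0.09 (one missing item) to −0.28 (three) on the literal item reading, and 0 to −0.04 on the likely intended reading. These sizes depend on the assumed mean-item total and patient levels; the arm shifts of 0.01 to 0.06 depend also on the assumed arm sizes. The responder flip is a constructed case at the threshold. The gap at Week 0 does not depend on any of these assumptions.

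Only the descriptive AQLQ summaries are affected, for forms with a permitted number of missing items. The primary endpoints are untouched. It is worth correcting because the line fixes how a secondary endpoint is derived and the correction is cheap.

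**What to change.** First check the line against the source file for a lost label. Then, before AQLQ is derived, replace it with one rule for every visit including Week 0. Preferably pro-rate over the answered items, as the plan already does for ACQ-5. State that the total is the mean of the items, and keep the existing limits on missing answers.

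If the previous-visit ratio is kept, write: missing item = (sum of items answered at this visit / sum of the same items at the previous visit) × that item's previous response. Limit the result to the item's permitted range; with the ratio 5/4.5 = 1.11 above, an item previously at its maximum would otherwise exceed it. Pro-rate where no earlier response exists. This option mixes two methods between Week 0 and later visits, which is why a single pro-rating rule is preferable.

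The cost is one or two lines of SAP text and a small programming change, with no new data.

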12.7.2.1. Handling of Missing and Partial Dates

Element	Reporting Detail
General	
 • Partial dates will be displayed as captured in subject listing displays.
Adverse	
 • The eCRF allows for the possibility of partial dates (i.e., only month and year) to be

Events	
recorded for AE start and end dates; that is, the day of the month may be missing. In such a case, the following conventions will be applied for calculating the time to onset and the duration of the event:
 
 ○ Missing Start Day: First of the month will be used unless this is before the start date of study treatment; in this case the study treatment start date will be used and hence the event is considered On-treatment as per Appendix 4: Study Phases and Treatment Emergent Adverse Events. ○ Missing Stop Day: Last day of the month will be used, unless this is after the stop date of study treatment; in this case the study treatment stop date will be used. ● Completely missing start or end dates will remain missing, with no imputation applied. Consequently, time to onset and duration of such events will be missing.
Concomitant Medications/ Medical History	
 ● Partial dates for any concomitant medications recorded in the CRF will be imputed using the following convention: 
 ○ If the partial date is a start date, a '01' will be used for the day and 'Jan' will be used for the month ○ If the partial date is a stop date, a '28/29/30/31' will be used for the day (dependent on the month and year) and 'Dec' will be used for the month. ● The recorded partial date will be displayed in listings.

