2. SUMMARY OF KEY PROTOCOL INFORMATION

2.1. Changes to the Protocol Defined Statistical Analysis Plan

Changes from the originally planned statistical analysis specified in the protocol are outlined in [Table 1](#).

Table 1 Changes to Protocol Defined Analysis Plan

Protocol	Reporting & Analysis Plan	
Statistical Analysis Plan	Statistical Analysis Plan	Rationale for Changes
Primary and secondary endpoints to be analysed.	All endpoints to be summarised only.	Enrolment into the 207972 study was terminated early due to the

[figure not shown]
Protocol	Reporting & Analysis Plan	
Statistical Analysis Plan	Statistical Analysis Plan	Rationale for Changes
		feasibility of completing the study in a timely manner, resulting in insufficient subjects for analysis to be performed.
An internal Safety Review Committee (iSRC) was to review safety data after the 20 th randomised subject received their first post-dose ECG/24hr Holter. A potential interim analysis, end of treatment analysis and final SAC analysis was due to be performed.	No iSRC analysis and only one final SAC analysis to be performed.	The study was unable to recruit the 20 randomised subjects required for the iSRC prior to termination. In addition, as recruitment was terminated early, and would not inform internal decision making, there was no requirement to report at multiple timepoints to align with portfolio decisions.
Primary, secondary and exploratory endpoints to be reported.	Primary and secondary endpoints only to be reported.	As there is insufficient data to draw any conclusions on exploratory endpoints, and they are not required for external disclosure, no outputs will be created.

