24 hour Holter		X	X ¹						Holter monitor needs to be returned to the clinic at end of 24 hour recording (i.e. the next day). ¹ Place the Holter 30-60mins prior to dosing
Vital signs	X	X	X ¹		X ¹	X ¹	X	X	1. Test to be performed prior to the 12-lead ECG (pre-dose and post dose)
AE review			←=====→						
SAE review	X	X	←=====→						At V1 and V2 collect only SAEs considered as related to study participation.
Concomitant medication review	X	X	←=====→						

EW: Early Withdrawal. The list of assessments listed in this column should be completed for an early withdrawal visit.

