12.4. Appendix 4: Study Phases and Treatment Emergent Adverse Events

12.4.1. Study Phases

Assessments and events will be classified according to the time of occurrence relative to study treatment start date.

Study Phase	Definition
Pre-Treatment	Date ≤ Study Treatment Start Date
On-Treatment	Study Treatment Start Date < Date ≤ Study Treatment Stop Date + 28 days
Post-Treatment	Date > Study Treatment Stop Date + 28 days

Completion of study epochs will be defined as the following:

Study Phase	Definition of Completion
Run-in	Randomised into study and received first dose of study treatment
Treatment	Completed Week 12 visit
Follow up	Completed 12 week follow-up period

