12.4.3. Treatment Emergent Flag for Adverse Events

Flag	Definition
Treatment Emergent	
If AE onset date is on or after treatment start date & on or before treatment stop date + 28 days.
 
Study Treatment Start Date ≤ AE Start Date ≤ Study Treatment Stop Date + 28 days

NOTES:

- If the study treatment stop date is missing then the AE will be considered to be On-Treatment.

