12.10.6. Safety Tables

Safety: Tables					
No.	Population	IDSL / Example Shell	Title	Programming Notes	Deliverable [Priority]
Adverse Events (AEs)					
3.01.	SAFF	SAFE_T01	Overview of On-treatment Adverse Events During the Study		SAC
3.02.	SAFF	AE1	Summary of All On-treatment Adverse Events by System Organ Class and Preferred Term	ICH E3	SAC
3.03.	SAFF	AE1	Summary of All On-treatment Serious Adverse Events by System Organ Class and Preferred Term	ICH E3	SAC
3.04.	SAFF	AE3	Summary of All On-treatment Adverse Events by Overall Frequency	ICH E3, summarise by PT	SAC
Laboratory: Chemistry					
3.05.	SAFF	LB1	Summary of Worst Case Chemistry Results Relative to Normal Range Post-Baseline Relative to Baseline	ICH E3	SAC
Laboratory: Hematology and Cardiac Markers					
3.06.	SAFF	LB1	Summary of Worst Case Hematology and Cardiac Markers Results Relative to Normal Range Post-Baseline Relative to Baseline	ICH E3	SAC

Safety: Tables					
No.	Population	IDSL / Example Shell	Title	Programming Notes	Deliverable [Priority]
ECG and Holter					
3.07.	SAFF	EG1	Summary of ECG Findings	IDSL	SAC
3.08.	SAFF	EG11	Summary of Maximum Increase in QTcF Values Post-Baseline Relative to Baseline by Category	IDSL	SAC
3.09.	SAFF	HM1	Summary of Holter Interpretations	IDSL	SAC
Vital Signs					
3.10.	SAFF	VS1	Summary of Vital Signs	ICH E3	SAC
3.11.	SAFF	VS1	Summary of Change from Baseline in Vital Signs	ICH E3	SAC
3.12.	SAFF	VS1	Summary of Change from Pre-dose to Post-dose in Vital Signs	ICH E3	SAC

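### The missing-day rules for adverse events lack a same-month condition on the start date and a floor at onset on the stop date

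*SAP*

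**What the plan says.** SAP Section 12.7.2.1 sets two conventions for adverse events recorded with month and year but no day.

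- **Start day missing:** "First of the month will be used unless this is before the start date of study treatment". When it is before, "the study treatment start date will be used and hence the event is considered On-treatment", with a reference to Appendix 4.
- **Stop day missing:** "Last day of the month will be used, unless this is after the stop date of study treatment". When it is after, the treatment stop date is used.

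Appendix 4 then classifies the imputed date in two ways. Section 12.4.3 flags an event as treatment emergent as follows: "If AE onset date is on or after treatment start date & on or before treatment stop date + 28 days". Section 12.4.1 defines Pre-Treatment as "Date ≤ Study Treatment Start Date", which includes the start date itself.

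On what is collected before dosing, the schedule in Section 12.2.1 says: "At V1 and V2 collect only SAEs considered as related to study participation". Those visits are at Days −28 and −14. Other adverse events appear to be reviewed only from V3.

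Tables 3.01 to 3.04 in Section 12.10.6 are all restricted to on-treatment events, including Table 3.03, "Summary of All On-treatment Serious Adverse Events by System Organ Class and Preferred Term". On study size, Section 2.1 states: "The study was unable to recruit the 20 randomised subjects required for the iSRC prior to termination".

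**The concern.** Moving an onset of unknown day to treatment start is a reasonable conservative convention when the recorded month is the month of first dose, because the event could have begun on either side of dosing. The rule does not stop there. Its only condition is that the first of the recorded month precedes treatment start, and that is also true of every earlier month. In those months the record already shows that the event came before dosing, and the rule overwrites a known fact. A serious event from screening or run-in could then be reported as occurring on treatment.

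The stop rule has a similar gap. It caps the imputed date at treatment stop without checking when the event began. Follow-up runs to Day 169 and the treatment-emergent window extends 28 days past treatment stop, so events that start or resolve after treatment stop are expected. Those that start later get an impossible interval. Those that start earlier and resolve in follow-up are cut off at treatment stop.

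**Working it through.** The SAP gives no figure to reproduce and no formula for event duration. I assume duration = stop − start + 1.

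**Start rule, worked case** (illustrative dates)
- First dose 10 March 2019, so nominal Day −28 is 10 February 2019. Serious event: start recorded as February 2019, stop known to be 20 February 2019.
- 1 February is before 10 March, so the imputed start is 10 March 2019.
- Section 12.7.2.1 calls it on-treatment and Section 12.4.3 flags it as treatment emergent. Section 12.4.1 would class the same date as Pre-Treatment.
- Duration: 20 Feb − 10 Mar + 1 = −18 + 1 = −17 days.
- With a same-month condition, the start is 1 February 2019 and the event is not treatment emergent.

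**How often the lead-in crosses a month boundary**
- Assume first-dose dates spread evenly over the 365 days of 2018 and a 28-day lead-in: 365 × 28 = 10,220 pre-dose days.
- A first dose on day k of a month (k = 1 to 28) has 29 − k of its 28 preceding days in an earlier month. Summed over k this is 28 × 29 / 2 = 406 per calendar month, and 406 × 12 = 4,872.
- 4,872 / 10,220 = 47.7%. A missing-day start on any of these 4,872 days is flagged treatment emergent under the current rule, and on none under the same-month condition.
- This is a share of calendar days, not a rate of events or of partial dates.

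**Weight of one case**
- At most 19 subjects were randomised: 1/19 = 5.3%. The tables use the dosed Safety population, which cannot be larger, so 5.3% is a lower bound.
- The allocation is not given. If 19 were split 10/9, one case is 1/10 = 10% or 1/9 = 11.1% of an arm.

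**Stop rule, general result**
- Let S be treatment stop and A a known onset with A > S. The event cannot end before A, so the last day of its stop month is on or after A and hence after S. The cap always applies, the imputed stop is S, and S < A.
- Duration = S − A + 1. For A = S + 1 it is 0; for A = S + 28, the last treatment-emergent day, it is −27. Neither depends on S.

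**Stop rule, by reading of the stop date** (the SAP does not define it)

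| Treatment stop | Onset Day 70 | Onset Day 120 |
|---|---|---|
| Day 57 (last planned dose) | 57 − 70 + 1 = −12 | 57 − 120 + 1 = −62 |
| Day 85 (end of treatment visit) | not reversed | 85 − 120 + 1 = −34 |

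In calendar terms: first dose 14 September 2018, last dose 9 November, onset 22 November (Day 70), stop recorded as November 2018. The current rule gives 9 November and −12 days. Month end, uncapped, gives 30 November and 30 − 22 + 1 = 9 days.

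If the start day is missing as well, the imputed start moves to the first of its month and the reversal is no longer certain. Over the same assumed year, with stop at Day 57 and both dates in one month, it still occurs in 35,507 of 40,880 combinations (87%).

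**The case against.** The effect on reported results is small and may be nil.

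- **The start rule needs a rare conjunction.** The event must be serious, related to study participation, recorded without a day, dated in a month before the dosing month, and in a subject who was still dosed. The SAP shows no such case. This stands, and it limits the size of the problem. The percentages above are what one event would add, not an expected distortion.
- **The stop rule changes no display.** No listed table reports event duration or time to onset, listings show partial dates as captured, and the treatment-emergent flag uses onset only. This also stands.
- **The conventions are introduced only for time to onset and duration.** This does not stand for the start rule, because the same sentence goes on to assign on-treatment status.
- **A miscount would be visible and errs towards over-counting.** True: the serious-event listings and the exposure listing would show the mismatch. But the table would then disagree with the listing behind it.
- **Under Section 12.4.1 the imputed event would be Pre-Treatment and so excluded.** This makes the miscount less certain. However, Section 12.7.2.1 expressly says on-treatment and Section 12.4.3 agrees. The conflict also affects every Day 1 event and needs its own correction.

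**Conclusion.** The concern holds, and the wording should be corrected. The start rule carries the point: it can place a serious event known to precede dosing in the on-treatment tables. Affected cases would be few. In a descriptive report on at most 19 randomised subjects, one such case is at least 5.3% of subjects, or about 10 to 11% of an arm under an assumed 10/9 split. The stop rule is certain to give a stop before the start for any event with a known onset after treatment stop and a missing stop day, whether treatment stop means Day 57 or Day 85, but it affects derived durations only.

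The reading of the text is firm. The practical effect cannot be estimated, because the frequency of partial dates is unknown.

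**What to change.** Replace the two conventions in Section 12.7.2.1:

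- **Start day missing:** use the treatment start date only if the recorded month and year are those of treatment start and any known stop date is on or after it. Otherwise use the first of the recorded month.
- **Stop day missing:** use the last day of the recorded month. Cap it at study completion, withdrawal or death only when that date falls in the recorded month, and never set it before the event's start date.

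This keeps the conservative assignment where the month leaves the timing open. Separately, make Sections 12.4.1 and 12.4.3 agree on a date equal to treatment start; otherwise an event properly imputed to that date still has two classifications.

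The date rules cost two sentences of SAP wording and one edit to the adverse event date derivation. No new data are needed.
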